11. PRODUCT USE BEHAVIOUR

On Days 1, 2, 3, and 4, subjects will use the product assigned according to the randomisation scheme under controlled conditions followed by a 4-hour *ad libitum* product use session with the same study product. Each subject will be provided with a new/unused Pulze HT device for each day of HT product use. The time each product is dispensed will be documented; products that stop functioning will be replaced and the failure documented.

The number of cigarettes smoked, as appropriate, will be documented from Check-in until beginning of smoking abstinence (Day -1, until at least 12 hours prior to the start of morning controlled product use on Day 1; Days 1 through 3, 8 hours post morning controlled use session IP start until at least 12 hours prior to the start of morning

Imperial Brands PLC
Project No. NER01/0004
Celerion Project No. CA35183

controlled product use scheduled on the following day). The number of cigarettes smoked and the number of HT sticks used will be documented during each 4-hour *ad libitum* product use session (Days 1 through 4).

The number of inhalations and reasons for missed puffs will be documented, as applicable.

The number of HT sticks used (*ad libitum* product use session), the number of CCs smoked (Days -1 through 4), and the number of puffs (morning controlled product use session) will be listed by subject and summarised by product, sex, and overall using descriptive statistics, including n, mean, SD, CV%, SEM, minimum, Q1, median, Q3, maximum, and 95% CI.

12. SAFETY

All case report form (CRF) data will be listed by subject and chronologically by assessment time points. This will include rechecks, unscheduled assessments, and early termination.

Applicable continuous variables will be summarised using n, mean, SD, minimum, median, and maximum.

The level of precision will be presented as follows: minimum/maximum in the same precision as in the database, mean/median in one more precision level than minimum/maximum, SD in one more precision level than mean/median, and n will be presented as an integer. Percentages will be presented as an integer.

Where individual data points are missing because of dropouts or other reasons, the data will be summarised based on reduced denominators.

12.1 Subject Discontinuation

The number of subjects enrolled, number who completed the study, and number who did not complete the study (overall and reasons for early withdrawal) will be tabulated by randomised sequence and overall. The number of subjects who received each study product and who did not receive study product at each study day will be tabulated. Subjects only enrolled in the product trial and dropped prior to randomisation will be summarised separately.

12.2 Demographics

Descriptive statistics will be reported for continuous variables (age, weight, height, and BMI) and frequency counts will be tabulated for categorical demographics variables (sex, ethnicity, and race). Summarization will be done by randomised sequence and overall. Subjects only enrolled in the product trial and dropped prior to randomisation will be summarised separately. Screen failure subjects will be listed.

Imperial Brands PLC
Project No. NER01/0004
Celerion Project No. CA35183

Age will be derived by subtracting the year of birth from the year of informed consent. If year of informed consent – year of birth is less than the protocol minimum age then the age derivation will be year of informed consent – year of birth +1.

12.3 Smoking History and Usual Brand Attributes

Smoking history and usual brand attributes will be summarised with descriptive statistics for continuous variables. Frequency counts will be presented for categorical variables. The continuous variables will include number of cigarettes smoked per day, number of years of cigarettes smoked, and the categorical variables will include usual cigarette brand, brand style, and flavour. Subjects only enrolled in the product trial and dropped prior to randomisation will be summarised separately.

12.4 Adverse Events

AE will be coded (to the preferred term) with Medical Dictionary for Regulatory Activities (MedDRA®) Version 24.1.

A study product use-emergent adverse event (PUEAE) is defined as an AE that is starting or worsening at the time of or after study product administration. Each PUEAE will be attributed to a product based on the onset date and time of the AE. AEs occurring prior to the first product use episode on Day 1 but after the product trial has started on Day -1 will be attributed to the product trial.

All events captured in the database will be listed in by-subject data listings. However, only PUEAEs will be summarised.

Frequencies of subjects with PUEAEs, regardless of relationship to study product will be summarised by study product and sorted by system organ class and preferred term. The number of PUEAEs will be tabulated in a similar manner. Tables which summarize the number of PUEAEs and number of subjects with PUEAEs by severity and relationship to study product will also be included.

Subjects only enrolled in the product trial and dropped prior to randomisation will be summarised separately.

Serious adverse events (SAEs), if present, will also be listed. Applicable narratives will be included in the CSR.

12.5 Clinical Laboratory Tests (Serum Chemistry, Hematology, Urinalysis)

Clinical laboratory evaluations will be performed at Screening, Day -1, and at End-of-Study (EOS) or upon early termination.

Out-of-normal range flags will be recorded as follows: high (H) and low (L) for numerical results and did-not-match (*) for categorical results. Out-of-range values and corresponding recheck results will be listed.

Imperial Brands PLC
Project No. NER01/0004
Celerion Project No. CA35183

For all numeric laboratory values, descriptive statistics will be presented for each laboratory test by assessment time point except for screening. Change from baseline will be summarised in a similar manner. Baseline is defined as the result closest and prior to the first product use on Day 1 which may include unscheduled or recheck results. This will typically be the result collected on Day -1. Post-product-use unscheduled events or rechecks will not be included in summaries. Similarly early termination results will not be included in summaries.

For each laboratory test, a shift table will be developed to compare the frequency of the results at baseline (above normal, normal, or below normal) with the respective post product use results. For urinalysis tests, the categories are normal and outside normal

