- b: Subjects will be admitted to the CRU on Day -1, at the time indicated by the CRU, and will remain confined until completion of study procedures on Day 4. Subjects may be admitted earlier than Day -1 for COVID-19 testing not related to study protocol as per CRU requirements. Check-in procedures include: identification, luggage check, questionnaire on study prohibitions, and subject orientation.
- c: To be updated at Check-in as necessary.
- d: Symptom-driven physical examinations may be performed at other times, at the Investigator or designee's discretion.
- e: Samples for serum chemistry will be obtained following a fast of at least 8 hours, however, in case of dropouts or rechecks, subjects may not have fasted for 8 hours prior to the serum chemistry sample being taken. For the samples collected at EOS, an 8-hour fast is not required.
- f: To be performed prior to discharge or prior to early termination from the study.
- g: To be performed prior to the start of each morning product use session.
- h: On Day 1, subjects will be randomised to 1 of 4 sequences.
- i: Subjects will participate in a Product Trial where they will consume one HT stick (flavour chosen by subject).
- j: Subjects will use the assigned study product under controlled conditions (i.e., completely use a single unit of the assigned study product, with puffs taken at 30-second intervals and puffs 3 seconds in duration), with Hour 0 as the start time of product use.
- k: On Days 1 through 4, subjects will use their randomised product (same product as the morning session) *ad libitum* for 4 hours starting after the 4-hour PK blood draw.

- l: The number of cigarettes smoked, as appropriate, will be documented from Check-in until beginning of smoking abstinence (Day -1, until at least 12 hours prior to the start of morning controlled product use on Day 1; Days 1 through 3, 8 hours post morning controlled use session IP start until at least 12 hours prior to the start of morning controlled product use scheduled on the following day). The number of cigarettes smoked and the number of HT sticks used will be documented during each 4-hour *ad libitum* product use session (Days 1 through 4).
- m: The number of inhalations and reasons for missed puffs will be documented.
- n: To be performed approximately 5 minutes prior to the start of the product use session.

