4.3.3 Meals/Dietary Considerations

For all subjects, meals and snacks will be provided at the appropriate times during confinement at the CRU. Each meal and/or snacks served at the CRU will be standardised and will be similar in caloric content and composition and will be taken at approximately the same time on each day. When confined in the CRU, subjects will be required to fast from all food and drink except water between meals and snacks.

Subjects will fast for at least 1 hour prior to and for at least 4 hours after the start of each controlled morning product use session on Days 1, 2, 3, and 4. Lunch will be served at approximately the same time on Days 1 through 4, at the start of the 4-hour *ad libitum* product use session (after collection of the 4-hour PK blood sample). After lunch, subjects will fast for the remainder of the 4-hour *ad libitum* product use session.

During confinement, water will be allowed *ad libitum*, except that subjects may not consume beverages of any kind (including water) during the morning product use sessions on Days 1, 2, 3 and 4. An exception to the water restriction can be made if a subject starts coughing uncontrollably while smoking or using the study products.

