6.4.4.5 Clinical Laboratory

All clinical laboratory tests will be conducted by an accredited laboratory. Values for the clinical laboratory parameters are to be within the laboratory normal ranges or deemed not clinically significant in the opinion of the Investigator. All tests listed below will be performed as delineated in the Study Events Flow Chart ([Table 1](#)). Up to approximately 38 mL of blood will be drawn from each subject during the entire study for clinical laboratory tests.

Serum Chemistry¹

- Albumin
- Alkaline phosphatase
- Alanine aminotransferase
- Aspartate aminotransferase
- Bicarbonate
- Blood urea nitrogen
- Creatinine
- Glucose
- Potassium
- Sodium
- Total protein
- Uric acid

Urinalysis²

- Bilirubin
- Blood
- Glucose
- Ketones
- Leukocyte esterase
- Nitrite
- pH
- Protein
- Specific gravity
- Urobilinogen

Additional Tests

- Serology
 - HIV
 - HBsAg
 - HCV
- Serum pregnancy test³
- Serum FSH⁴
- Urine cotinine
- Urine drug screen
 - Amphetamines
 - Cannabinoids
 - Cocaine
 - Opiates
- Urine/breath alcohol

Hematology

- Hematocrit
- Hemoglobin
- Platelet count
- Red blood cell count
- White blood cell count with differential

¹ Serum chemistry tests will be performed after at least an 8-hour fast; however, in case of dropouts or rechecks, subjects may not have fasted for 8 hours prior to the serum chemistry sample being taken. For the samples collected at EOS, an 8-hour fast is not required.

² A microscopic examination for red blood cells, white blood cells, bacteria, and casts will be performed if an abnormality is noted in leukocyte esterase, protein, blood, or nitrite.

³ Human chorionic gonadotropin (females only).

⁴ For postmenopausal females only.

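### Serum chemistry is normally fasted at baseline but need not be at end of study, and the SAP's change and shift tables ignore this, so any meal effect on glucose would be mixed into the pooled post-use change

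*SAP*

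**What the plan says.** **Fasting rule.** Footnote e of the Study Events Flow Chart (Protocol Table 1) states: "Samples for serum chemistry will be obtained following a fast of at least 8 hours". It allows for dropouts and rechecks that are not fasted, and then makes an exception for the final sample, as does footnote 1 of Protocol 6.4.4.5: "For the samples collected at EOS, an 8-hour fast is not required". Glucose is one of the listed serum chemistry tests.

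**Laboratory time points and baseline.** SAP 12.5: "Clinical laboratory evaluations will be performed at Screening, Day -1, and at End-of-Study (EOS) or upon early termination". On baseline: "Baseline is defined as the result closest and prior to the first product use on Day 1 which may include unscheduled or recheck results". The SAP expects this usually to be the Day -1 result.

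**Summaries.** All numeric laboratory values get descriptive statistics by time point, and "Change from baseline will be summarised in a similar manner". In addition: "For each laboratory test, a shift table will be developed to compare the frequency of the results at baseline" with the results after product use. In the shells for Tables 14.3.5.1 and 14.3.5.2, EOS is the only time point after baseline and subjects are pooled over products. The first shell also has means outside the reference range flagged.

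**Meals on Day 4.** Protocol 4.3.3: "Lunch will be served at approximately the same time on Days 1 through 4". Lunch comes at the start of the 4-hour ad libitum session, after the 4-hour PK sample, and subjects then fast until the session ends. EOS tests are due before discharge, with no clock time fixed.

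**The concern.** A change from baseline can be interpreted only if the two samples were taken under comparable conditions. Here the protocol itself makes the conditions differ for a test that responds to meals, and the SAP treats the two samples as alike. SAP 12.5 and the two shells contain no fasting flag, footnote or exception. The protocol amendment carrying the waiver is dated 29 October 2021 and the SAP 13 January 2022. SAP section 13 lists one departure from the protocol, on topography.

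The tables have one baseline column and one later value, with no unexposed group. If lunch raised glucose, the rise would sit in a column headed post-use and could not be separated from a change after product use. Tolerability and safety is a stated secondary objective, and Protocol 1.2 reports no earlier clinical studies of these products, so the safety tables should not carry an avoidable ambiguity.

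**Working it through.** The documents give no figure on this point, so there is nothing to reproduce. The check has three parts.

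**1. Fasting status of the two samples**

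| Sample | Rule | Use in SAP 12.5 |
|---|---|---|
| Day -1, scheduled | fast of at least 8 h | usual baseline |
| Recheck before first use | may be unfasted | may replace the Day -1 value as baseline |
| EOS, scheduled | 8 h fast waived | only post-use value in both tables |
| Recheck or unscheduled sample after use, early termination | may be unfasted | left out of the summaries |

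The usual comparison is therefore fasted against possibly unfasted.

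**2. Time from lunch to the EOS sample**

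- Lunch begins at about hour 4 and the ad libitum session ends at about hour 8: 8 − 4 = 4 h.
- The serum chemistry listing shell (Appendix 16.2.8.1) shows a Day 4 sample at hour 8.67. This is a layout value, not a scheduled time: 8.67 − 4 = 4.67 h.
- Shortfall against an 8-hour fast: 8 − 4 = 4 h, or 8 − 4.67 = 3.33 h.
- A subject who eats the scheduled lunch cannot be 8 hours fasted before about hour 4 + 8 = 12.
- Food between hour 8 and the sample would shorten the interval. It is neither scheduled nor excluded for this test.

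**3. Illustration of size (every value assumed except n = 24)**

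Let X be baseline and Y the EOS glucose, in units of the fasting between-subject SD. They are bivariate normal with SD 1 and correlation 0.5 or 0.8. The reference limits are ±1.96. There is no product effect, and the meal adds d to the mean of Y. The expected mean change in Table 14.3.5.1 is then d itself. The expected number of normal-to-high shifts is 24 × P(−1.96 ≤ X ≤ 1.96 and Y > 1.96), found by simulation with one million draws per setting.

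| Meal shift d | Normal to high, correlation 0.5 | Normal to high, correlation 0.8 |
|---|---|---|
| 0 | 0.49 | 0.33 |
| 0.25 | 0.89 | 0.69 |
| 0.5 | 1.51 | 1.29 |

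As a plausibility check, all high EOS values at d = 0.5 number 24 × [1 − Φ(1.96 − 0.5)] = 24 × 0.072 = 1.7, which must exceed the count that was also normal at baseline (1.5 or 1.3). At d = 0 the total is 24 × 0.025 = 0.6, against 0.5 or 0.3.

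**The case against.** The best reply is that the effect may be negligible and the tables carry little weight. Much of this stands.

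- Subjects fast from lunch to the end of the session, so the sample may come 4 hours or more after eating. The documents do not show the direction or size of a glucose effect at that interval. The waiver permits an unfasted sample but does not require one.
- The tables are descriptive, with no test, confidence interval or product column. Completers have used all four products by EOS. An uncontrolled before-and-after comparison could not establish a product effect even with matched fasting.
- SAP 2.2 leaves the laboratory summaries some room for clinical judgement, and sample times are listed by subject.

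What does not fall away is that the comparison is between unlike samples by rule, and the reader of the table is not told.

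A reader might go further and infer that several subjects will be falsely flagged high. Assume fasting glucose of mean 4.9 and SD 0.45 mmol/L, and a fed shift of 0.3 to 0.5 mmol/L with 0.3 mmol/L of added spread, so the EOS SD is √(0.45² + 0.3²) = 0.54. The share high is then 23 to 36% at a limit of 5.6 and 7 to 13% at 6.0, or about 2 to 9 of 24. The documents do not support this as a forecast. None of these values appears in them, and the shifts (0.3/0.45 = 0.67 to 0.5/0.45 = 1.1 SD) leave out small or zero effects. Part of the rise comes from the added spread alone: with no shift the shares are already 9.8% and 2.1%. The calculation also counts all high EOS values rather than normal-to-high shifts. The reference ranges are not given either, so whether the glucose limit is specific to fasting is unknown.

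**Conclusion.** The point holds as a minor reporting fault. SAP 12.5 and Tables 14.3.5.1 and 14.3.5.2 set a normally fasted baseline against an EOS value that need not be fasted, and any meal effect on glucose would be mixed into the pooled post-use change. Under assumed shifts of 0 to 0.5 fasting SD, about 0.5 to 1.5 of 24 subjects would move from normal to high with no product effect (0.3 to 1.3 at the higher correlation). The lower end is what arises with no meal effect at all.

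This rests on the EOS sample being drawn after the ad libitum session, which the schedule suggests but does not fix, and on the assumed normal model. A reader might also infer that every baseline is fasted, that a spurious rise would be charged to one product, or that other analytes are equally affected. The documents do not support these readings: a recheck used as baseline may be unfasted, the tables pool over products, and glucose is the only analyte for which a case is made. The PK endpoints and product comparisons are untouched.

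**What to change.** In SAP 12.5 and the shells for Tables 14.3.5.1 and 14.3.5.2:

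1. Label EOS serum chemistry as possibly non-fasted.
2. Show glucose by time point as observed, and leave it out of the change-from-baseline and shift summaries unless both samples had the same fasting status.
3. List time since last meal only where it is recorded.
4. Keep all other analytes as planned.

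Whether to fast before the EOS sample is a matter of conduct for the sponsor and is not part of this proposal.

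The cost is SAP and shell wording, and the loss of a glucose change figure for most subjects. Neither document says that fasting status or actual meal times are captured at each sample. If they are not, the like-for-like exception in item 2 could not be applied and glucose would be reported as observed values only.

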12.6 Vital Signs

Vital signs (blood pressure, heart rate, respiration rate, and body temperature) will be measured for safety purposes at Screening, Check-in (Day -1), prior to the product use on Days 1-4, and at EOS or upon early termination.

Descriptive statistics will be reported for vital sign measurements (blood pressure, heart rate, respiration rate, and body temperature) by time point except for screening. Change from baseline will be summarised in a similar manner. Baseline is defined as the result closest and prior to the first product use on Day 1 which may include unscheduled or recheck results. This will typically be the result collected prior to study product use on Day 1. Post-product-use unscheduled events or rechecks will not be included in summaries. Similarly early termination results will not be included in summaries.

12.7 Electrocardiogram

Electrocardiogram will be performed at Screening, Day -1, and at EOS or upon early termination.

Descriptive statistics will be presented for each ECG parameter by assessment time point except for screening. Change from baseline will be summarised in a similar manner. Baseline is defined as the result closest and prior to the first product use on Day 1 which may include unscheduled or recheck results. This will typically be the result collected on Day -1. Post-product-use unscheduled events or rechecks will not be included in summaries. Similarly early termination results will not be included in summaries.

ECG data will be listed by subject and assessment timepoint. QTcF values that are > 450 msec and increase from baseline > 30 msec will be flagged in the data listing.

Imperial Brands PLC
Project No. NER01/0004
Celerion Project No. CA35183

12.8 Concomitant Medications

All concomitant medications recorded during the study will be coded with the WHO Dictionary Version 01SEP2021 b3 and listed.

12.9 Oral and Physical Examination

Oral and physical examinations will be performed at Screening. Symptom-driven physical examinations may be performed at other times, at the Investigator or designee's discretion. Physical examinations will be listed by subject. Abnormal findings will be discussed in the CSR.

12.10 Exhaled CO

Exhaled CO will be performed at Screening and Day -1.

Exhaled CO data will be listed by subject and assessment timepoint.

12.11 Device Malfunction

Incidence of device malfunction(s) will be listed by subject and tabulated by product.

13. SUMMARY OF CHANGES FROM PROTOCOL-PLANNED ANALYSIS

The analyses described in this SAP are aligned with those analyses described in the protocol except the following items:

- Per protocol, the summarization of puff topography parameters will be based on by study product, study day, overall and by sex, usual brand cigarette flavour (non-menthol or menthol), age, number of years smoking, CPD, and time point. Some of the variables are not applicable for summarization of topography parameters. The topography parameters will be summarised by study product, sex, and overall.

14. SUMMARY TABLES AND FIGURES

Summary tables and figures are numbered following the International Conference on Harmonization (ICH) structure but may be renumbered as appropriate during the compilation of the tables and figures for the CSR. Note that summary tables and figures will be generated using SAS® Version 9.4.

The following is a list of table and figure titles that will be included in Section 14 of the report. Table and figure titles may be renumbered as appropriate during the compilation of the report.

Imperial Brands PLC
 Project No. NER01/0004
 Celerion Project No. CA35183

